### **Figure 2. Outcome Measure Assessments Time points**

Outcomes: All testing will occur at the SNF by facility PTs, PTAs, OTs or a trained CNA (blinded). Primary Outcome: **Gait speed** will be measured by the time it takes to walk a 4-meter path. Time will be measured with a stopwatch to the nearest hundredth of a second. This measure was selected as the primary outcome because: 1) it has been shown to predict risk of mobility and physical disability, higher health care utilization and increased mortality; 2) it has been established as a meaningful outcome measure in older persons with a wide range of conditions; 3) it is a valid and reliable measure; 4) it is easily understood by patients, their families, providers and health care policy makers (good face validity); and 5) it is easily performed in the home and well tolerated by patients varying in condition and degree of health. Secondary Outcomes: The **Timed Up And-Go (TUG)** test will be performed on each patient as a measure of basic mobility skill and evaluation of fall risk. The TUG test well established cut-off scores to indicate falls in both frail and community dwelling older adults. The TUG has excellent inter-rater reliability, and is responsive to changes in mobility status. The **Short Physical Performance Battery (SPPB)** is a well-accepted global measure of lower extremity function, which consists of walking speed, chair stands, and balance. It is a well-studied composite measure and a strong predictor of disability, institutionalization, and morbidity in older adults. The test takes ~10-15 minutes to administer and was designed to be administered in a setting with limited space. The battery has an excellent safety record as it has been administered to well over 10,000 persons in various studies. The SPPB components and total score are derived from normative values obtained from a population-based study. The reliability of the individual components, as well as the summary score of the SPPB, are good with intra class correlation coefficients (ICC) >0.88 and good sensitivity to change. The continuous scoring system minimizes ceiling effects and scores range from 0-12 with higher scores indicative of better performance.

Numbers and reasons for hospitalizations and emergency room visits during the SNF stay will be documented by treating therapists. Falls will also be counted and documented by

treating therapists or nursing staff. Falls will be defined as an unintentional change in position resulting in coming to rest on the ground or other lower level.

Covariates, clinical and background characteristics. Information on other patient characteristics to describe the patient population and interpret results will be obtained from facility medical records; all data will be de-identified. These characteristics include age; gender; race; history of comorbidities, medications, primary diagnosis for hospital admission; length of skilled nursing facility stay; complications in hospital and length of stay.

Qualitative data will be collected through voluntary focus group discussions consisting of therapists in the SNFs with current IRB approval (Brookdale Mountain View, Veterans Community Living Center at Fitzsimons, PowerBack Rehabilitation, Gardens on Quail, Good Sam-Ambassador, Villa St. Louis Park). The data collected will inform future refinement of the PMC program for large-scale dissemination.

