
## I. Hypotheses and Specific Aims:

**Specific Aim 1:** To determine if the group in the post-PMC training period demonstrates better physical function, as measured by *gait speed* (primary outcome), timed-up-and go test (TUG), and the Short Physical Performance Battery (SPPB) compared to pre-PMC training period.

Hypothesis 1: Patients in the post-PMC training period will demonstrate greater improvements in gait speed, TUG, and SPPB at time of discharge from SNF (primary endpoint) compared to the group in the pre-PMC training period.

**Specific Aim 2:** To determine if the group in the post-PMC training period demonstrates improved rates of discharge to the community from SNF facilities and lower hospital re-admission rates compared to pre-PMC training period.

Hypothesis 2: Following the post-training PMC period, patients will demonstrate higher rates of discharge to the community and have a lower frequency of hospital re-admissions during SNF stay compared to the pre-PMC training period.

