#### **B. Description of Population to be Enrolled:**

Patients will be enrolled from four SNFs in the Denver metro area: **Gardens on Quail, Brookdale Mountain View, Veterans Community Living Community at Fitzsimons, and Powerback Rehabilitation; and two in Minnesota: Good Sam-Ambassador and Villa St. Louis Park.** All patients temporarily residing in the designated SNFs will receive the current standard of care during the 5-month pre-PMC training period. Outcomes data will be collected for all patients who are admitted and discharged during the 5-month pre-PMC training period. Once SNF staff have been trained on the PMC protocol (2-month period), all patients will receive the PMC intervention (post-PMC training period) as the new standard of care per therapist discretion, unless contraindicated. Outcomes data will be collected for all patients who are admitted and discharged during the 5month post-PMC training period. All patients will receive the respective intervention (current standard of care or PMC) until discharge from the SNF. Outcomes data will only be collected on patients who fit the inclusion criteria: adults older than 18 years of age who are admitted to a skilled nursing facility and receive at least physical or occupational therapy. Exclusion criteria: Patients with neurological disorders, such as a stroke or traumatic brain injury, will be excluded as the best practice for managing these patients is based on motor-control theory versus the proposed progressive strengthening and aerobic approach. Patients on hospice care will be excluded as hospice care is focused on palliative needs and not rehabilitation. Other patients to be excluded will include those with conditions where strength training is contraindicated (as indicated by the American College of Sports Medicine Guidelines for Exercise Testing and Prescription): recent unstable fractures, advanced congestive heart failure (ejection fraction <30%), bone metastasis sites, tumors in strengthening target areas, acute illness, recent myocardial infarction (within 3-6 weeks), weight bearing restrictions on graft or fracture sites, exposed tendon or muscle, absence of pedal pulses, presence of a fistula, and platelet levels <50,000/ $\mu$ L.

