#### **F. Data Analysis Plan:**

##### Analysis

[figure not shown]
**Primary and Secondary Outcomes:** **The primary outcome (Aim 1) for this study is the change in gait speed between admission and discharge from a SNF. The change in gait speed will be pooled across the six facilities for the two respective time periods (pre and post PMC training).** The mean **change in gait speed** for the independent group of patients tested during the pre-PMC training period will be assessed and compared to the mean change in gait speed for the independent group of patients during the post-PMC training period.

Secondary outcomes include physical function measures (SPPB, TUG) and health care utilization outcomes (emergency room visits, falls, skilled nursing home length of stay, and re-hospitalizations), which will be recorded weekly and at discharge from SNF. Preliminary descriptive and graphical analyses (including boxplots, scatterplots, profile plots to examine change over time) will be used for data cleaning and visualization of primary and secondary outcomes.

**Primary Analysis:** The primary analysis will be an intent-to-treat comparison of change in gait speed from SNF admission to discharge between 2 independent groups of patients (pre and post-PMC training groups). Statistical inference regarding the difference between pre and post-PMC training groups will be based on independent sample t-tests. Comparisons will be made on changes in outcome measures (admission to discharge)

within pre/post PMC training groups. Groups of patients will be pooled from all facilities to form 2 independent samples for comparison of time periods (pre and post PMC training) (See Figure 3). The conclusion about the statistical significance of differences between pre/post groups will be determined by this single statistical test to protect against an elevated risk of false positive conclusions.

**Figure 3.** Data analysis plan

**Secondary Analyses (Aim 2):** We will estimate health care utilization outcomes rates (falls, emergency department visits, skilled nursing home length of stay or re-hospitalizations) for each pre/post PMC training period and compare rates between arms using a likelihood ratio test.

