The characteristics of the time trajectory (weekly and at discharge from SNF) for treatment effects will also be analyzed in secondary analyses to inform the development of methods to improve long-term outcomes. The analytic methods will include maximum likelihood estimates from a repeated measures model of the mean effect of gait speed at each of the measurement times. The trend in means will be evaluated using a linear contrast as the summary measure of greatest interest. This approach will evaluate whether there are differences in the first-order trends (slope) between the pre/post PMC training groups. The evaluation of the time trajectory will be conditioned on the stratification variables and the baseline value of gait speed.

The qualitative study will be conducted after quantitative data collection for the parent study has been completed to better understand the process of implementation for future refinement of the program. The audio from the focus group discussions will be transcribed either by two study team members or by Transcription Outsourcing. Two coders will review the transcription and develop a code book in an iterative process until both coders reach agreement. Coded transcripts will be analyzed to identify barriers and facilitators to implementation of PMC.

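### TUG change in seconds is undefined for patients unable to do the test at either visit, and the plan has no rule that keeps them in the comparison

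*Combined protocol and SAP*

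**What the plan says.** - **Hypothesis (section I).** Patients in the later period "will demonstrate greater improvements in gait speed, TUG, and SPPB at time of discharge from SNF".
- **Measurement (section IV.A, under Figure 2).** The TUG "test will be performed on each patient as a measure of basic mobility skill and evaluation of fall risk". Section IV.A schedules it in the first day or two after admission, then weekly and at discharge. SPPB is given a 0 to 12 score. TUG is given no ceiling time, category or score for a patient who cannot do it.
- **Entry (section IV.B).** Data are collected on "adults older than 18 years of age who are admitted to a skilled nursing facility and receive at least physical or occupational therapy". Ability to stand or walk is not required. Exclusions such as weight-bearing restrictions and unstable fractures remove some non-walkers, but not all.
- **Analysis (section IV.F, Primary Analysis).** "Statistical inference regarding the difference between pre and post-PMC training groups will be based on independent sample t-tests", and "Comparisons will be made on changes in outcome measures (admission to discharge"). Both sentences stand under the primary analysis, but they speak of tests and outcome measures in the plural. The opening summary also describes the analysis as two-sample t-tests. No other method is given for TUG.
- **What covers gait speed only.** The intent-to-treat sentence reads "The primary analysis will be an intent-to-treat comparison of change in gait speed from SNF admission to discharge". The longitudinal analysis uses "maximum likelihood estimates from a repeated measures model of the mean effect of gait speed at each of the measurement times". Neither names TUG, and no missing-data rule is stated.

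**The concern.** A t-test on change needs a time at both visits. A patient who cannot rise, walk and return has no time, so the change is undefined. That removes three groups from the comparison: patients unable throughout, patients who regain the ability (the clearest success a mobility programme can have), and patients who lose it (the clearest failure). For a patient able at admission, being analysed depends on the discharge result, which PMC is meant to change. TUG is one of the three function measures on which Aim 1 rests, so a TUG result confined to patients able at both visits does not answer the hypothesis as worded.

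**Working it through.** **1. Figures in the plan.** There is no SD, effect size, unable rate or power statement for TUG. The only power statement (92 per group, 90%) is for gait speed, so there is no TUG figure to reproduce.

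**2. Who can contribute a change in seconds.**

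| Admission | Discharge | Change in seconds | Enters the t-test |
|---|---|---|---|
| able | able | defined | yes |
| able | unable | undefined | no |
| unable | able | undefined | no |
| unable | unable | undefined | no |

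**3. Share with no change.** Let a be the share unable at admission and l the share of the others unable at discharge. The share with no change is a + (1 − a)l. Both inputs are assumptions. The 602 per period is the collection cap in section IV.A.

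| a | no change, l = 0 to 5% | left of 602 |
|---|---|---|
| 10% | 10 to 14.5% | 542 to 515 |
| 20% | 20 to 24% | 482 to 458 |
| 30% | 30 to 33.5% | 421 to 400 |
| 40% | 40 to 43% | 361 to 343 |

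Simulations in which l follows from the model give roughly 11 to 47%. Those ends correspond to l = (0.11 − 0.10)/0.90 = 1% and l = (0.47 − 0.40)/0.60 = 12%.

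**4. Difference between periods.** Patients unable at admission are out in both periods whatever happens later. With equal a, the difference is therefore (1 − a)(l_pre − l_post). Illustration: admission speed normal with SD 0.20 m/s, unable below 0.20 m/s, usual gain 0.13 (SD 0.20), PMC effect 0.14 for everyone, 6 m course, 400,000 per arm.
- Mean 0.45 m/s (10.5% unable at admission): both times available in 85.1% pre and 88.4% post, so 14.9% v 11.6% are left out, a difference of 3.3 points.
- Mean 0.35 m/s (22.6% unable): 71.9% and 75.9%, so 28.1% v 24.1% are left out, a difference of 4.0 points.

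Other assumed settings gave differences from about 1 point upwards.

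**5. Successes not counted.** If 30% of those unable at admission regained the ability pre and 50% post (assumed), the regainers left out are 602 × a × 0.30 v 602 × a × 0.50. That is 18 v 30 at a = 10% and 72 v 120 at a = 40%.

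**6. Extreme case.** Same model, with PMC helping only patients unable at admission. The share of all patients regaining ability rose from 6.0% to 8.4% (mean 0.45) and from 12.1% to 17.1% (mean 0.35). The difference in TUG change among patients with both times was 0.00 s and −0.02 s. When everyone benefited it was −2.16 s and −2.44 s.

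**7. Power, illustrative.** Completers' seconds v 1/TUG with unable = 0, under three sets of assumed effects:

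| Effect | Set A | Set B | Set C |
|---|---|---|---|
| additive in speed, 10 to 40% unable | 42–58% v 82–93% | 34–43% v 64–82% | 29–41% v 60–82% |
| proportional in seconds, 10% unable | 64–72% v 67–73% | 51% v 54% | 59% v 63% |
| proportional in seconds, 40% unable | 44–48% v 66–72% | 35–38% v 51–55% | 45% v 65% |

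Set A used two-sided 5% tests with 92, 200 or 361 per period. At a fixed effect, 44% power with 92 per period would be about 76% with 200, so the flat ranges mean that the effect was scaled to n. Only the contrast within a cell is informative. Type I error stayed near 5% (about 3 to 7% in set B).

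**The case against.** - **Exclusion is inferred.** A reader might infer that the plan says unable patients are dropped. It does not; it is silent. But an undefined change cannot enter the stated test, and any other handling would be a choice made after the data are seen.
- **The power loss is not general.** A reader might infer that the TUG test loses much of its power whatever the setting. At 10% unable with a proportional effect the two analyses are almost level. The additive-speed model also favours 1/TUG by construction. This stands.
- **Bias is not shown.** Every unable rate is assumed, and neither the size nor the direction of any bias can be taken from the documents. Skewness of TUG seconds is not documented either, and the simulated type I error gives no ground for calling the t-test invalid. This stands.
- **TUG is secondary.** The significance conclusion rests on one test, of gait speed. SPPB covers walking, chair stands and balance from a score of 0, so Aim 1 is not blind to regained ability. This stands and limits the importance of the point. It does not repair the TUG comparison, and the plan does not say that SPPB replaces TUG for these patients.
- **Gait speed has the same silence.** The documents do not say that a non-walker scores 0 m/s, so gait speed cannot be held up as already settled.

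**Conclusion.** The point holds as a defect in a secondary comparison. Followed as written, the TUG analysis can describe only patients able at both visits. It omits everyone who regains or loses the ability, and whether a patient able at admission is included depends on the discharge outcome. With 10 to 40% unable at admission, roughly 11 to 47% have no TUG change. The gap between periods is about 1 to 4 points if PMC works and admission case mix is the same in both. A benefit confined to patients unable at admission could be missed entirely. The power loss ranges from small to large with the assumed unable rate and form of effect, and the absolute power values should not be relied on. The documents do not support a claim that the TUG result is biased in a known direction, or that the primary conclusion is affected. The plan should be changed, but the trial's main inference does not depend on it.

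**What to change.** 1. On the existing assessment form, code 'unable' (attempted or judged unable, with reason) separately from 'not done'.
2. Prespecify one TUG comparison that keeps unable patients: either change in 1/TUG with unable = 0, compared by the planned t-test, or a rank-based comparison with unable as the worst rank. Choose one before the outcome data are examined. 'Not done' stays missing and is counted by period.
3. Tabulate unable-to-able and able-to-unable transitions by period.
4. Report change in seconds among completers descriptively, labelled as such.

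The cost is a paragraph of analysis text and one extra form code, with no new visits or tests. For records already collected, 'unable' may not be recoverable; blanks that cannot be classified should be reported by period. The small downside is a less familiar, composite scale that mixes ability with speed. The descriptive seconds and the transition table let a reader separate the two.

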#### **B. Description of Population to be Enrolled:**

Patients will be enrolled from four SNFs in the Denver metro area: **Gardens on Quail, Brookdale Mountain View, Veterans Community Living Community at Fitzsimons, and Powerback Rehabilitation; and two in Minnesota: Good Sam-Ambassador and Villa St. Louis Park.** All patients temporarily residing in the designated SNFs will receive the current standard of care during the 5-month pre-PMC training period. Outcomes data will be collected for all patients who are admitted and discharged during the 5-month pre-PMC training period. Once SNF staff have been trained on the PMC protocol (2-month period), all patients will receive the PMC intervention (post-PMC training period) as the new standard of care per therapist discretion, unless contraindicated. Outcomes data will be collected for all patients who are admitted and discharged during the 5month post-PMC training period. All patients will receive the respective intervention (current standard of care or PMC) until discharge from the SNF. Outcomes data will only be collected on patients who fit the inclusion criteria: adults older than 18 years of age who are admitted to a skilled nursing facility and receive at least physical or occupational therapy. Exclusion criteria: Patients with neurological disorders, such as a stroke or traumatic brain injury, will be excluded as the best practice for managing these patients is based on motor-control theory versus the proposed progressive strengthening and aerobic approach. Patients on hospice care will be excluded as hospice care is focused on palliative needs and not rehabilitation. Other patients to be excluded will include those with conditions where strength training is contraindicated (as indicated by the American College of Sports Medicine Guidelines for Exercise Testing and Prescription): recent unstable fractures, advanced congestive heart failure (ejection fraction <30%), bone metastasis sites, tumors in strengthening target areas, acute illness, recent myocardial infarction (within 3-6 weeks), weight bearing restrictions on graft or fracture sites, exposed tendon or muscle, absence of pedal pulses, presence of a fistula, and platelet levels <50,000/ $\mu$ L.

Up to 30 therapists will be recruited from the Gardens on Quail, Brookdale Mountain View, Veterans Community Living Center at Fitzsimons, Powerback Rehabilitation, Good Sam-Ambassador, and Villa St. Louis Park staff who have been trained in the PMC intervention.

Inclusion criteria: Trained in PMC intervention, provided PMC intervention to patients at Gardens on Quail, Brookdale Mountain View, Veterans Community Living Center at Fitzsimons, Powerback Rehabilitation, Good Sam-Ambassador, and Villa St. Louis Park.  
Exclusion criterion: Decline to participate.

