## **IV. Research Methods**

### **A. Outcome Measure(s):**

During both the pre-PMC and post-PMC training periods, a trained Certified Nursing Assistant (CNA) (blinded) will assess gait speed, TUG, and SPPB within 24-48 hours of admission to SNF. If the CNA is unable to assess within 24-48 hours of admission, then the physical therapist performs the assessments. The occupational therapist will administer the Mini Mental Status Scale to assess baseline cognitive status within 24-48 hours of admission to SNF. A trained CNA (blinded) will continue to perform functional assessments (gait speed, TUG, SPPB) weekly and at discharge from SNF (Figure 2). Physical therapists (PTs) and physical therapist assistants (PTAs) will perform weekly and discharge assessments as necessary.

Interventions: During the 5-month pre-PMC training period (baseline), all current patients at the SNF will receive usual care treatment as facility therapists will practice per current standard of care. We will collect pre-PMC training data for 3 months or until collection of data on 602 patients (half the number of patients approved to be consented) (Figure 1). Therapists will then be trained on the PMC intervention for 2 months. After training, the facilities and individual therapists will decide how to implement such care at their discretion. Following the training period, we will collect post-PMC training data for 5 months or until collection of data on 602 patients (half the number of patients approved to be consented) (Figure 1). The data collected in all facilities during the pre-PMC training period will be pooled into one group to dilute the effect of facility variability. The data collected during post-PMC training period will be pooled in the same way.

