### C. Study Design and Research Methods

This study is a preliminary investigation using a pre-post training design in six SNFs (Figure 1). We will pool the data across the six SNFs into the pre and post-PMC training periods to dilute the effect of facility variability. Given that the average length of stay in a SNF is 21 days, the pre/post PMC training design will consist of two independent samples of patients to include only those that were admitted and discharged within a given period. As we get interest from additional facilities, we may submit an addendum to include them. Additional sites would help inform sample size estimates for a potential future, cluster-randomization study design. During the 5-month pre-PMC training period, the rehabilitation therapists will treat patients per the current standard of care and a trained CNA (blinded) or PT/PTA (as necessary) will collect outcomes data at admission, weekly, and at discharge. Then, training on the PMC intervention will occur over a 2-month period. Any patients admitted or discharged in the SNF during the PMC training period will not be used. During the 5-month post-PMC training period, therapists will implement the PMC protocol and collect outcomes data as indicated previously (Figure 1).

The medical records will provide information on prior level of function, age, other medical conditions, **re-hospitalization** and **emergency room visits**, medications, sex, admitting diagnosis, **falls**, SNF length of stay, **discharge location**, evaluation and treatment documentation.

Five focus group discussions of 4-6 therapists each will follow an interview guide and last a duration of approximately 1 hour. Therapist participation is voluntary, and all participants will be asked for informed consent. Discussions will be recorded and transcribed for content analysis.

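### The focus-group criteria require therapists to have delivered PMC, so trained therapists who never delivered it are excluded from the study of barriers to implementation

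*Combined protocol and SAP*

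**What the plan says.** The therapist part of section IV.B begins with a recruitment sentence: "Up to 30 therapists will be recruited from the Gardens on Quail" and five other facilities, drawn from "staff who have been trained in the PMC intervention". Two inclusion criteria follow: "Inclusion criteria: Trained in PMC intervention, provided PMC intervention to patients at Gardens on Quail" and the same five other facilities. The only exclusion is "Exclusion criterion: Decline to participate".

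Section IV.C gives the format: "Five focus group discussions of 4-6 therapists each will follow an interview guide". Section IV.A describes the members more loosely, as volunteers among the therapists at the approved facilities, and says that the material will be used to refine PMC for wider dissemination. The analysis text in section IV.F states the purpose: "Coded transcripts will be analyzed to identify barriers and facilitators to implementation of PMC".

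On use of PMC after training, section IV.A says: "After training, the facilities and individual therapists will decide how to implement such care at their discretion". The patient part of section IV.B likewise makes PMC the new standard of care subject to therapist discretion.

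**The concern.** The qualitative work asks what helped and what hindered the uptake of PMC. The plan allows uptake to vary between therapists, and then makes some uptake a condition of being asked. This is selection on the outcome to be explained. A site that applies the criteria literally must turn away a trained therapist who never started PMC, although that person can say what stopped it from being started.

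At stake is how complete the list of barriers will be. An obstacle strong enough to prevent any delivery may be under-reported or missed, and the program would then be refined for dissemination without it. The gait-speed comparison and the other patient outcomes do not depend on who sits in the focus groups.

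**Working it through.** The point concerns eligibility, so most of the check sets the passages side by side.

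1. *Who may enter.* The recruitment sentence in IV.B asks for one thing, training in PMC. The inclusion criteria ask for two, training and delivery to patients. Section IV.A asks only that the person be a therapist at an approved facility. The criteria are the narrowest of the three statements and are the operative rule, and neither broader statement removes the delivery requirement.

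2. *Can a trained therapist have delivered nothing?* The discretion in IV.A and IV.B permits it. The documents do not say how often it is expected.

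3. *Who is excluded.* The delivery criterion has no minimum number of patients, duration or fidelity.
   - Regular, partial or rare use: eligible.
   - Tried and stopped: eligible.
   - Trained, no delivery at all: not eligible.

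4. *Is there another route?* No separate group, interview or survey is described for trained therapists who delivered nothing.

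5. *Do the stated numbers agree?* Five groups of 4 to 6 give 5 × 4 = 20 to 5 × 6 = 30 therapists. The upper end matches the stated maximum of 30.

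6. *Size.* Let q be the share of trained therapists who never delivered PMC. The documents give no value for q, so the shares below are assumptions. If n places were filled in proportion from all trained therapists, the expected number of never-users is n × q:

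| Assumed q | n = 20 | n = 30 | Under the written criteria |
|---|---|---|---|
| 10% | 2 | 3 | 0 |
| 25% | 5 | 7.5 | 0 |
| 40% | 8 | 12 | 0 |

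The last column follows from the rule at any q. The others only show how the loss would scale. If q is 0, nothing is lost.

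**The case against.** The strongest reply is that the excluded group may be very small or empty. Section IV.A speaks of deciding how to implement PMC, which is not plainly a choice of whether to. Section IV.B says that all patients will receive PMC in the post-training period, section IV.C says that therapists will carry out the protocol, and section IV.D notes that some physical therapists already work on its principles. Over five months, few trained therapists may have delivered none of it. This stands as a limit on size: the documents permit never-use but do not predict how much. It does not rescue the criterion. If everyone delivers PMC, the criterion does nothing; if some do not, it removes them.

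A second reply is that therapists who used PMC little, or gave it up, can describe barriers well. This also stands. A reader might infer that the groups will hear only from committed adopters and only about barriers that were overcome. The text does not support that, because any delivery qualifies.

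A third reply is that the groups are a small voluntary add-on to a study that calls itself preliminary. That is fair, and it bounds the importance of the point. A reader might go further and say that the rule removes the best explanation for a null gait-speed result. The documents do not support this either: the groups are planned to inform refinement, not to measure delivery or explain the primary result, and treatment documentation is among the medical-record data in section IV.C.

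A reader might also object to the timing, since "The qualitative study will be conducted after quantitative data collection for the parent study has been completed". The sample-size section shows that one facility had not yet begun collecting data, but gives no start dates, so no delay can be worked out. Waiting is also defensible, because it keeps discussion at early facilities from influencing delivery at later ones. One group per facility would not fit five groups across six facilities.

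**Conclusion.** The point holds in a limited form. The inclusion criteria exclude, by rule, trained therapists who never delivered PMC from a study meant to identify barriers to delivering it, and they are narrower than the recruitment sentence directly above them. Partial, rare and discontinued users are not excluded. This rests on reading the two listed criteria as joint conditions and on taking the discretion clauses to permit never-use.

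The size of the excluded group cannot be determined from the documents; the 10% to 40% range is illustrative. The consequence is confined to the qualitative component. It merits correction because the rule works against its stated aim and can be changed cheaply, not because it threatens the trial's main result.

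**What to change.** In the therapist inclusion criteria of section IV.B, delete the requirement to have provided PMC, so that every therapist trained in PMC at the six facilities is eligible. This also brings the criteria into line with the recruitment sentence. Record each participant's level of PMC use (none, some then stopped, partial, regular) so that barriers can be read against it. Seek to include never-users and low users where they exist. A fixed quota in every group is not advisable, because the number of such therapists at each facility is unknown.

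The five groups of 4 to 6, the ceiling of 30 and the schedule stay as they are. The cost is a short eligibility amendment and one added item of information per participant. There is a small downside: therapists who did not use PMC may be harder to recruit, and some places will go to people with less experience of delivering it.
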